Thorough review of safety information relevant to the use of MIN-101 indicates that MIN-101 is generally safe and well tolerated, with the most frequently reported TEAEs being headache, anxiety, asthenia, and insomnia in patients with schizophrenia. None of the "classical" side effects generally associated with the currently marketed typical or atypical antipsychotic treatments were observed, such as sedation, prolactin and weight gain increases, or extrapyramidal symptoms. QT prolongation was observed in clinical trials with MIN-101. The risk for QT prolongation is dose related, the main driver for QT prolongation being BFB-520 plasma levels. In the MIN-101C03, 2 patients receiving the highest dose (64 mg) of MIN-101 MR formulation, presented with a significant increase in QTcF. These 2 patients were found to be outliers for BFB-520 levels and were identified within the first 4 weeks of treatment.

To mitigate the risks of antipsychotic discontinuation, patients who entered this trial will be closely followed by the treating/research team by frequent face to face visits and phone calls between visits. This will enable the treatment/research team to intervene promptly as soon as patients experience symptomatic worsening or display behaviors that endanger themselves or others.

To mitigate the risk for QT prolongation, a new formulation will be used in the present study that was developed to specifically avoid the presence of high levels of drug and metabolite concentrations while resulting in the same bioavailability (AUC) observed with the formulation used in the Phase 2b study, which resulted in positive treatment effect.

The following measures have also been implemented in the protocol to further mitigate the risk for QT prolongation:

- Only CYP 2D6 extensive metabolizer patients, will be enrolled.
- Drugs likely to increase QT as well as drugs inhibiting CYP 2D6 and CYP3A4/5 (likely to increase MIN-101 and BFB-520 levels) are not allowed during study participation.
- Exclusion of patients with known personal or familial history of QT prolongation (including congenital long QT syndrome), or with recent acute myocardial infraction, or with uncompensated heart failure.
- Exclusion of patients presenting with risk factors such as hypokalemia, hypomagnesemia, hypocalcemia or bradycardia.
- Close monitoring of the patients, who will be hospitalized during the first 2 days of treatment.

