- 16. Current systemic infection (e.g., Hepatitis B, Hepatitis C, HIV, tuberculosis). Patients with positive Hepatitis B core antibody test and negative HBsAg may be included in the study if aminotransferase levels (ALT/SGPT and AST/SGOT do not exceed 2 times ULN.
- 17. Patient who requires or may require concomitant treatment with any other medication likely to increase QT interval (e.g., paroxetine, fluoxetine, duloxetine, amiodarone).
- 18. Patient who requires medication inhibiting CYP 2D6 or CYP 3A4.
- 19. Patient with a clinically significant ECG abnormality that could be a safety issue in the study, including QT interval value corrected for heart rate using QTcF > 430 msec for males and > 450 msec for females.

- 20. Patient with a history of myocardial infarction based on medical history or ECG findings at Screening.
- 21. Familial or personal history of long QT syndrome or with additional risk factors for Torsade de Pointes.
- 22. Patient whose safety laboratory results show one or more of the following: potassium < 3.4 mmol/L, or calcium < 2.07 mmol/L, or magnesium < 0.70 mmol/L.
- 23. Patients with unexplained syncope.
- 24. Woman of child-bearing potential, or man, who are unwilling or unable to use accepted methods of birth control.
- 25. Woman with a positive pregnancy test, is lactating, or is planning to become pregnant during the study.
- 26. Patient who participated in another clinical study within 3 months prior to Screening, or received MIN-101 previously, or has previously participated in > 2 clinical studies with experimental medication within the past 2 years (previous participation in 3 clinical studies with experimental medication will require approval of the sponsor before eligibility is determined).

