#### 4.3. **Prohibitions and Restrictions**

In general, concomitant medications with primary CNS activity, as well as CYP 2D6 and CYP 3A4/5 inhibitors and concomitant medications likely to increase QT interval are not allowed in this study (refer to Attachment 1). The following are examples of prohibited medications/therapies during the study:

- Oral or injectable antipsychotic medications other than study drug medication
- Depot antipsychotic medication
- Clozapine
- ECT
- VNS
- r-TMS
- Antidepressants
- Lithium

Patients should be discontinued from the study if any of the above prohibited medications are used during the study (the Sponsor's Responsible Medical Officer can allow exceptions).

For a complete list of prohibited therapies, please refer to Attachment 1 (Allowed and Prohibited Concomitant Medications). Of note, grapefruit and Seville oranges (and their juices) are CYP 3A4 inhibitors and must not be consumed during the study.

Additional restrictions include female patients of childbearing potential, and men, who are unwilling to use an accepted method of contraception during the course of the study.

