# 9.3. Stopping Rules

In addition, specific stopping rule criteria for a patient's withdrawal are described below:

- 1. Increase from Baseline in PANSS total score of 25% and an increase of 3 points or more on the hallucinations, suspiciousness/paranoia, hostility, delusions, or uncooperativeness PANSS items.
- 2. CGI-S worsening of more than 2 points.
- 3. Suicidal ideations or behavior.
- 4. Occurrence of an AE, which may jeopardize the patient's health as per investigator opinion.

- 5. Worsening of psychotic symptoms or occurrence of any dangerous behavior against self or others as per investigator opinion.
- 6. Patient with significant increase in ALT (i.e., > 5 ULN).
- 7. Patient with abnormal laboratory results with simultaneous increases of total bilirubin (> 2 ULN), ALT or AST (> 3 ULN) with alkaline phosphatases (< 1.5 ULN).
- 8. Patient with sustained mean QTcF value > 500 msec (confirmed by a second ECG under strict resting position and at minimum at ½ hour [30 minutes] duration from the first measurement). Patient's treatment must be discontinued until mean QTcF values are obtained from the ECG central-reader. If values are confirmed, the patient must be discontinued from the study, else treatment is restarted at the discretion of the investigator.
- 9. Patient with sustained mean increase of > 60 msec in the QTcF compared to Baseline (confirmed by a second ECG under strict resting position and at minimum at ½ hour [30 minutes] duration from the first measurement). Patient's treatment must be discontinued until mean QTcF values are obtained from the ECG central-reader. If values are confirmed, the patient must be discontinued from the study, else treatment is restarted at the discretion of the investigator.
- 10. If the patient for any reason requires treatment with another therapeutic agent that has been demonstrated to increase the QT interval or inhibit CYP 2D6 or CYP 3A4. In this case, discontinuation from the study occurs prior to introduction of the new agent.
- 11. If the patient experiences a syncope or dizziness not explained by other known causes, such as documented orthostatic hypotension, Ménière disease, etc.
- 12. Patient has an overt seizure or reports seizure-like activity (loss of consciousness, uncontrollable tremor not due to EPS). A seizure or seizure like activity will be followed-up on-site using SAE follow-up forms, neurological examination, and EEG monitoring.

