### ATTACHMENT 1: ALLOWED/PROHIBITED CONCOMITANT MEDICATIONS

Drug Class	As	Chronic	Restrictions
	Needed	Use	
Analgesics	Y	N	Only non-opiate analgesics are allowed.
Anorexics	N	N	
Antacids	Y	Y	H2 antagonists and proton pump inhibitors not allowed,
Antianginal Agents	N	N	
Antiarrhythmics	N	N	
Antiasthma Agents	Y	Y	Inhaled agents only.
Antibiotics	Y	Ν	Some macrolides, quinolones and other antibiotics not allowed.(refer to the next table)
Anticholinergics	Ν	Ν	Only rescue medications are allowed (refer to protocol)
Anticoagulants	Ν	Y	Only aspirin (max. 325 mg/day) is allowed as chronic anti-platelet treatment.
Anticonvulsants	Ν	Ν	
Antidepressants	Ν	Ν	
Antidiarrheal Preparations	Y	Ν	
Antifungal Agents:			
- Systemic	Ν	Ν	
- Topical	Y	Y	
Antihistamines	Y	Ν	Only fexofenadine, loratadine, cetirizine are allowed.
Antihypertensives (*)	Ν	Y	Calcium channel blockers and ACE inhibitors allowed. Isradipine and nicardipine not authorized.
Anti-inflammatory Drugs	Y	Y	Systemic corticosteroids are not allowed.
Antinauseants	Y	Ν	Domperidone, droperidol, odansetron
Antineoplastics	Ν	Ν	
Antiobesity	Ν	Ν	
Antipsychotics	Ν	Ν	
Anxiolytics	N	Ν	Only rescue medication are allowed; see Section 4.4.2
Cough/Cold Preparations	Y	Ν	Use of cough and cold preparations containing pseudoephedrine or phenylpropanolamine is not permitted. Decongestants containing narcotics are not permitted. Dextrometorphan and codeine are not authorized
Diuretics	Ν	Y	Allowed if stable dose 1 month before enrollment. Furosemide, HCTZ not allowed (refer to next table)
H2-Blockers	N	N	
Hormones	Ν	Y	Only thyroid hormone replacement, oral contraceptives and estrogen replacement therapy are allowed.
Hypoglycemic Agents	Ν	Ν	
Hypolipidemics	Ν	Y	
Insulin	Ν	Ν	
Muscle Relaxants	Ν	Ν	
Psychotropic drugs not otherwise specified	Ν	Ν	No drugs with psychomotor effects or with anxiolytic, stimulant, antipsychotic, or sedative properties are
(including herbal products)			allowed.
Sedatives/Hypnotics	Ν	Ν	Zolpidem, zopiclone and zaleplon allowed

Note: All antihypertensives must be at stable dose >3 months prior to enrollment and must be continued at the same dose during the study.

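### Attachment 1's antihypertensives row permits calcium channel blockers that its own next table and exclusion 18 bar as CYP inhibitors

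*Protocol*

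**What the plan says.** Attachment 1 of the protocol has two parts. The first is a table by drug class, with a mark for as-needed use, a mark for chronic use, and a column of restrictions. Antihypertensives are marked no for as-needed use and yes for chronic use, with the restriction "Calcium channel blockers and ACE inhibitors allowed. Isradipine and nicardipine not authorized". A note under the table requires an antihypertensive to have been at a stable dose for more than three months before enrollment and to stay at that dose.

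The second part lists individual drugs in three columns: QT-prolonging drugs, CYP 2D6 inhibitors and CYP 3A4 inhibitors. Diltiazem and mibefradil appear in both CYP columns, verapamil in the CYP 3A4 column.

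The body of the protocol is consistent on inhibitors:

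- Section 4.2, exclusion 18: "Patient who requires medication inhibiting CYP 2D6 or CYP 3A4".
- Section 4.3: "CYP 2D6 and CYP 3A4/5 inhibitors and concomitant medications likely to increase QT interval are not allowed in this study". The section then adds "For a complete list of prohibited therapies, please refer to Attachment 1".
- Section 1.5, among the measures against QT prolongation: "drugs inhibiting CYP 2D6 and CYP3A4/5 (likely to increase MIN-101 and BFB-520 levels) are not allowed during study participation". The same section describes the QT risk as dose related, "the main driver for QT prolongation being BFB-520 plasma levels".
- Section 9.3, stopping rule 10, covers a patient who comes to need an agent that "has been demonstrated to increase the QT interval or inhibit CYP 2D6 or CYP 3A4"; in that case "discontinuation from the study occurs prior to introduction of the new agent".

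**The concern.** A row that permits a drug class and then names exceptions reads as complete. Someone checking a hypertensive patient's medication against this row would find calcium channel blockers permitted, would not find diltiazem or verapamil among the exceptions, and could conclude that the patient may enter and stay on the drug. The note on unchanged dosing would then tell the site to continue it.

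The rule at risk is one of the protocol's stated QT-safety measures. The sponsor expects these inhibitors to raise MIN-101 and BFB-520 levels. Section 1.5 reports that the two patients with a significant QTcF increase on 64 mg in the Phase 2b study were outliers for BFB-520. Section 1.4.2.1 reports very high BFB-520 concentrations in a CYP 2D6 poor metabolizer enrolled by error.

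There is a smaller cost to the data. Protocol Section 10.2 and SAP Sections 4.4 and 6 treat intake of prohibited medication as a possible major violation, so a patient enrolled on the strength of this row could be dropped from the per-protocol set.

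**Working it through.** No formula applies. The check sets the two parts of Attachment 1 side by side and then applies the rules in the body of the protocol.

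**Step 1. Drugs covered by the row's permission that also appear in the CYP columns.** That these are calcium channel blockers is general pharmacology.

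| Drug | Named as an exception in the row? | CYP 2D6 column | CYP 3A4 column | Entries |
|---|---|---|---|---|
| Diltiazem | No | Yes | Yes | 2 |
| Mibefradil | No | Yes | Yes | 2 |
| Verapamil | No | No | Yes | 1 |

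Entries: 2 + 2 + 1 = 5, for 3 drugs. Of the 3, the row names 0; its 2 exceptions are isradipine and nicardipine.

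**Step 2. Where the exceptions seem to come from.** The QT column has its own calcium channel blocker heading. Nicardipine is legible under it; the other entry is garbled in the text available to me but is consistent with isradipine. The likely explanation, which is an inference, is that the row was checked against the QT column and not against the two CYP columns.

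**Step 3. Which rule applies to which patient.** For a drug already taken at entry, exclusion 18 is the operative bar. Stopping rule 10 is worded for an agent about to be introduced, so it covers a later start. Both give the same answer for all three drugs: not allowed.

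**Step 4. Whether the conflict is resolved in writing.** Attachment 1 does not say which table governs when they differ. The antibiotics and diuretics rows refer to the next table; the antihypertensives row does not.

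**Step 5. Whether the pattern recurs.** Three other listed drugs fall in classes that the first table allows without a pointer: loperamide (QT list; antidiarrheals), celecoxib (CYP 2D6 list; anti-inflammatory drugs) and gestodene (CYP 3A4 list; oral contraceptives under hormones). Their class membership is again general pharmacology. A general precedence sentence would settle these as well.

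**The case against.** The strongest reply is that the rule already exists and is stated several times. Section 4 requires every eligibility criterion to be met, and a class-level permission in a medication table cannot waive an exclusion criterion. A patient on stable diltiazem should fail exclusion 18 before the unchanged-dose note can apply. Most rows of the class table have no pointer, so its absence here proves little. This all stands, and it limits the point to a contradiction that a careful reader can resolve. It does not make the row correct: the row names exceptions and omits three drugs that the same attachment lists as inhibitors.

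Other safeguards also count. The antianginal and antiarrhythmic rows are marked not allowed, which leaves hypertension as the route in. There are triplicate ECGs, QTcF stopping rules 8 and 9, blood samples for prohibited medication, and a patient study card naming excluded drugs. Their limits are that the QTcF rules act after prolongation has occurred, Section 3.1 says only that the samples may be assayed, and the sponsor consultation in Section 4 depends on someone having a question.

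Three stronger readings are tempting, and the documents do not support them:

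- A reader might infer that the protocol permits CYP inhibitors. It does not; Sections 1.5, 4.2, 4.3 and 9.3 bar them.
- A reader might infer that Section 4.3 sends sites to this row. It refers to Attachment 1 as a whole, which includes the inhibitor table naming all three drugs.
- A reader might see a second wrong permission in the antinauseants row, which names three drugs without saying whether they are allowed. Words may have been lost from that cell in the text available, and the QT list already includes all three drugs, so it is not part of this point.

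**Conclusion.** The antihypertensives row is wrong as written. It allows three drugs that the next table lists as CYP inhibitors and that exclusion 18, Section 4.3 and the QT-mitigation list rule out. The protocol as a whole prohibits them, so this is an internal contradiction confined to one row, with several backstops.

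Its size is 3 drugs and 5 list entries, none covered by the row's exceptions. The documents give no basis for estimating how many patients would be affected, and they do not show that anyone was or would be enrolled on such a drug. Sample size, power, type I error control and the analysis model are untouched. The one assumption is that diltiazem, verapamil and mibefradil are calcium channel blockers. Because the row bears on a stated QT-safety measure and costs almost nothing to correct, it should be corrected.

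**What to change.** Keep the row's opening permission and replace its list of exceptions with: *except isradipine, nicardipine, diltiazem, verapamil, mibefradil and any other drug listed in the next table (refer to next table)*.

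Add one sentence to Attachment 1: *Where the class table and the QT/CYP list differ, the QT/CYP list takes precedence.* This also settles loperamide, celecoxib and gestodene.

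The cost is the wording of one row, one added sentence and a notification to sites. Design, data collection and analysis do not change.

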### Key:

Red: known risk of TdP; Blue-bold: possible risk of TdP; Black: conditional risk of TdP: e.g., in case of overdose, DDI or electrolytes imbalance.

Drugs inducing QT prolongation	CYP 2D6 inhibitors	CYP 3A4 inhibitors
Anesthetic	Anti-infectives	Anti-infectives
Sevoflurane	Chloroquine	Chloramphenicol
Propofol	Quinacrine	Clarythromycin
	Cardiovascular	Ciprofloxacin
Anticonvulsivants	Amiodarone	Erythromycin
Ezogabine (retigabine)	Aprindine	Norfloxacin
Felbamate	Mibefradil	Telithromycin
	Propafenone	5
Anti-histamines	Labetalol	Anti-Viral
Diphenhydramine	Quinidine	Boceprevir
Hydroxyzine		Delvirdine
	Antidepressants	Indinavir
Anti-infectives	Amitriptyline	Nelfinavir
Amantadine	Citalopram	Ritonavir
Artenimol+ piperaquine	Clomipramine	Saquinavir
Azithromycin	Doxepin	Telaprevir
Bedaquiline	Duloxetine	1
Chloroquine	Escitalopram	Antifungal
Ciprofloxacin	Fluoxetine	Fluconazole
Clarithromycin	Fluvoxamine	Itraconazole
Delamanid	Paroxetine	Ketoconazole
Erythromycin	Sertraline	Voriconazole
Fingolimod		
Garenoxacin	Antipsychotics	Antidepressants
Gemifloxacin	Chlorpromazine	Fluvoxamine
Halofantrine	Fluphenazine	Nefazodone
hydrochloroquine	Haloperidol	Norfluoxetine
Levofloxacin	Levomepromazine	
norfloxacin	Perphenazine	Others
Metronidazole	Promethazine	Amiodarone
Moxifloxacin	Risperidone (weak)	Aprepitant
Ofloxacin	Sertindole	Cimentidine
Quinine	Thioridazine	Diltiazem
Roxithromycin		Gestodene
Telavancin	Others	Grapefruit juice
Telithromycin	Bupropion	Imatinib
	Celecoxib	Mibefradil
Antifungal	Cinacalcet	Mifepristone
Amphotericin B	Chlorpheniramine	Suboxone
Fluconazole	Cimetidine	Verapamil
Itraconazole	Clemastine	
Ketoconazole	cocaine	
Pentamidine	Codeine	
Posaconazole	Delavirdine	
Voriconazole	Dextropopoxyphene	
Antiviral	Diltiazem	

atazanavir	Dinhanhydromina	
	Dipnennydramine	
Liavirenz	Doxorubicin	
Nelfinavir	Entacapone (high doses)	
Ritonavir	Halofantrine	
Saquinavir	Hydroxyzine	
Telaprevir	Indinavir	
Voriconazole	Imatinib	
	Lobelin	
Cardiovascular:	Lomustine	
	Methadone	
Antianginal	Moclobemide	
Ivabradine	Metoclopramide	
Ranolazine	Midodrine	
	Moclobemide	
Antiarrhythmics	Nortuloxeline	
Amiodarone	Ranitidine	
Disopyramide	Ritonavir	
Dofetilide	Ticlopidine	
Dronedarone	Tripelennamine	
Flecainide	Vinblastine	
Ibutilide	Vincristine	
Pilsicainida	Vinorelbine	
Proceinamide	Vohimbina	
Quinidine	Tommonie	
Cotalal		
Solator		
Calaium Channal Plaakars		
Landinino		
Nicordinino		
Nicardipine		
Diuretics		
Bendorflumethiazide		
Furosemide		
Hydrochlorothiazide		
Indanamide		
Torasemide		
Torasennue		
Anti HTA		
ketanserin Moexinril/HCTZ		
Cholinesterase inhibitor		
Donepezil		
Galantamine		
Psychotropics:		
Antidepressants		

Confidential

A mitrintyline	
Citalonrom/osoitalonrom	
Cloimprainine	
cyamepromazine	
Desipramine	
Doxepin	
Imipramine	
Fluoxetine	
Fluvoxamine	
Mirtazapine	
Nortriptyline	
Paroxetine	
Sertraline	
Trazodone	
Trimipramine	
Venlafaxine	
Antipsychotics	
Aripiprazole	
Asenapine	
Chlorpromazine	
Clozapine	
Flupentixol	
Haloperidol	
Iloperidone	
levosulpride	
Melperone	
Olanzapine	
paliperidone	
Pimavanserin	
Pipamperone	
Pimozide	
Promethazine	
Prothinendyl	
Pernhenazine	
Quetianine	
Risperidone	
Sertindole	
Sulpiride	
sultopride	
Thioridazine	
ziprasidone	
Zotenine	
Zoupine	
Antimanic	
Lithium	
Littiituiii	

Confidential

Sedative, hypnotics	
Choral hydrate	
Devmedetomidine	
Deaneuctonnunc	
Antiemetics	
Domperidone	
Droperidol	
Ondansetron	
Granisetron/ Dolasetron.	
Tropisetron	
Metoclopramide	
······	
Others:	
Phospho-diesterase 3 inhibitor:	
Anagrelide	
cilostazol	
Protein kinase inhibitors: Lapatinib,	
Sunitinib, Bosutinib, Ceritinib,	
Crizotinib, Dabrafenib, Dasatinib,	
Lenvatinib, Nilotinib, Osimertinib,	
Pazopanib, Ribociclib, Sorafenib	
Apomorphine	
Alfuzosin	
Atomoxetine	
Capecitabine	
Cocaine	
Degarelix	
Esomeprazole	
Eribulin	
Famotidine	
Hydrocodone	
Ibogaine	
Lanzoprazole	
Leuprolide	
Levomethadyl	
Loperamide	
Methadone	
Mitepristone	
Mirabegron	
Necitumumab	
Nusinersen	
Umeprazole	
Oxytocin	
Pantoprazole	
Panobinostat	
Papaverine	

Pasireotide	
Romidepsin	
Solifenacin	
Tacrolimus	
Tamoxifen	
Terlipressin	
Terolidine	
Tetrabenazine	
Tiapride	
Tizanidine	
Tolterodine	
Toremifene	
Vandetanib	
Vardenafil	
Vemurafenib	
Vorinostat	

### ATTACHMENT 2: READINESS FOR DISCHARGE QUESTIONNAIRE

This tool is to be used for research purposes only and should not be utilized in determining actual eligibility for discharge

Note: The items below should be rated independently of social or economic factors.

Please circle your response to each question:								
1) The subject is not actively suicidal or homicidal.								
Strongly Agree	Agree	Disagree Strongly Disagree						
2) The subject has adequate control over aggression and impulsivity.								
Strongly Agree	Agree	Disagree	Strongly Disagree					
3) The subject has the ability	/ to carry out bas	sic ADLs (Activities of	daily living).					
Strongly Agree         Agree         Disagree         Strongly Disagree								
4) The subject has the ability to take medicine independently (from the hospital/medical staff).								
Strongly Agree	Agree	Disagree	Strongly Disagree					
5) The subject's delusions and hallucinations do not significantly interfere with functioning.								
Strongly Agree	Agree	Disagree	Strongly Disagree					
6) Does the subject have a 0	CGI-Severity of ≤	≤ 4 ? (see below)						
Yes	No							
• Rate the patient's CGI-Seven mentally ill is the patient at the	erity. Considerin his time?	g your total clinical ex l	perience with this population, how					
0 = Not assessed		4 = Moderately ill						
1 = Normal, not mentally ill		5 = Markedly ill						
2 = Borderline Mentally ill		6 = Severely ill						
3 = Mildly ill		7 = Among the most extremely ill patients						
• Using the above items as a guide only, please answer the following:								
Based on your clinical judgment of symptomatic improvement, and independent of social or economic factors, is this subject ready for discharge?								

